10.2 Timing and type of tumour assessments

A thorough clinical and radiological evaluation of malignancy, as judged appropriate by the Investigator, and in line with the protocol, must be performed before a patient receives their first dose of BT1718. The same methods that detect evaluable lesions at baseline must be used to follow these lesions throughout the trial. To ensure compatibility, the radiological assessments used to assess response must be performed using identical techniques. Imaging based evaluation is preferred to evaluation by clinical examination when both methods have been used to assess the anti-tumour effect of a treatment.

All radiological assessments must be performed within four weeks (28 days) before starting treatment with BT1718. The interval between the last anti-cancer therapy and these measurements must be at least four weeks. All clinical measurements to assess response must be performed within **one** week before the first dose of BT1718.

Complete responses (CR) and partial responses (PR) need to be confirmed by a subsequent assessment at least four weeks later. Stable disease criteria must be met at least once and at least six weeks after the initial dose of BT1718 is given to be defined as SD. There is no requirement for repeat assessments to be performed in order for the patient to be assigned a status of SD.

Copies of the scans must be available for external independent review if requested by the Sponsor.

10.2.1 Baseline evaluations

These must include radiological measurements of lesions in the chest, abdomen, and pelvis by CT scan or MRI scan and/or other radiological measurements as clinically indicated or clinical measurements as appropriate e.g. assessment of palpable lesions or measurement of tumour markers. Tumour marker data (if applicable) can add useful data in the clinical interpretation of radiological assessment, but does not have the validation of RECIST radiological assessment and will be treated as exploratory to support the interpretation of individual cases. All areas of disease present must be documented (even if specific lesions are not going to be followed for response) and the measurements of all measurable lesions must be recorded clearly on the scan reports. Any non-measurable lesions must be stated as being present. For clinical measurements, documentation by colour photography including a ruler to estimate the size of the lesion is strongly recommended, as this aids external independent review of responses (See Appendix 2 Section 1.2.1 of RECIST 1.1 criteria).

10.2.2 Evaluations during and at 'off-study'

Tumour assessments must be repeated Day 15 – Day 28 of every two cycles or more frequently, when clinically indicated. All lesions measured at baseline must be measured at every subsequent disease assessment, and recorded clearly on the scan reports. All non-measurable lesions noted at baseline must be noted on the scan report as present or absent.

All patients who are removed from the trial for reasons other than PD must be re-evaluated at the time of treatment discontinuation, unless a tumour assessment was performed within the previous four weeks.

It is the responsibility of the Principal Investigator to ensure that the radiologists are aware of the requirement to follow-up and measure every target lesion mentioned at baseline and comment on the non-target lesions in accordance with RECIST 1.1 criteria.

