3.1.2 Secondary objectives and endpoints

Secondary objectives	Endpoints
Dose escalation phase and expansion phase	
To investigate the pharmacokinetic (PK) behaviour of BT1718 in human	Measurement of C_{max} , AUC, terminal elimination half-life ($t_{1/2}$), and other PK parameters of BT1718 in plasma, both as an intact and cleaved molecule.
Dose escalation and expansion phase	
To assess preliminary signals of BT1718 efficacy in dose escalation and in relevant tumour types with high expression of membrane type 1 matrix	Assess anti-tumour response according to Response Evaluation Criteria in Solid Tumours (RECIST) Version 1.1.
metalloproteinase (MT1-MMP) in the expansion phase	Estimate progression-free survival, progression-free survival rate at six months, and OS (where available). Estimate duration of response.

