5.2.2 Phase I, dose escalation phase, Stage 2, dosing schedule/treatment schedule

In addition to evaluating a twice weekly dosing schedule in Stage 1 above, a once weekly dosing schedule will also be evaluated in Stage 2. Stage 2 will open at a dose where there is expectation of potential biological activity based on available PK, toxicity and/or PD data from Stage 1.

BT1718 will be administered intravenously once weekly for three out of four weeks (dosing on Days 1, 8 and 15 +/- 1 day). Each cycle of treatment will consist of 28 days and patients may continue until disease progression, depending on the availability of BT1718. The starting dose of the once weekly regime will be up to 100% of the overall weekly dose from the last completed cohort deemed safe from the twice weekly schedule (Phase I, Stage 1). Stage 2 will include a minimum of three evaluable patients following a 3+3 design.

Alternative dosing schedules may be considered by the Sponsor based on emerging data during the study, for example if the toxicology profile is benign with the twice weekly dosing regimen, continuous bi-weekly dosing maybe evaluated. Emerging data obtained during Phase I may be used in the decision to proceed with the Phase IIa stages. In addition, depending on the patient populations selected, an increased dosing frequency may also be considered. If any changes are made to the dosing schedule a substantial amendment will be submitted to the MHRA, REC and HRA for approval.

Phase I of the trial has completed.

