5.5 Dose modifications

5.5.1 Dose delays and reductions

Patients who experience a DLT (defined in Cycle 1 only) that resolves to Grade \leq 1 or recovers to baseline within 15 days of the start of the DLT may recommence treatment, with the agreement of the PI, Sponsor and patient. The dose should be reduced to a lower dose level. If the AE has not resolved to Grade \leq 1 or recovered to baseline within 15 days, the patient will be taken off-study. If the patient experiences a DLT at this reduced dose, either the same or different toxicity, there will be no further dose reductions and the patient will be withdrawn from the study.

Haematological toxicities

- Patients who experience a ≥Grade 3 haematological toxicity will have the subsequent doses omitted during that cycle until the toxicity resolves to <Grade 3. On resolution to <Grade 3, treatment can recommence at the same dose level during that cycle.
- If a clinically significant Grade 2 toxicity related to BT1718 (probably or highly probably) is still present when a patient is due to start the next cycle, that cycle should be delayed up to 14 days until the toxicity resolves to ≤Grade 1.
- The first time a dose is omitted or delayed, it may be given at the same dose the next time. However, if there is a subsequent need to omit or delay again, the dose should be reduced to a lower dose level (unless, in exceptional circumstances, the PI, Sponsor and patient agree that further dose omissions/delays are appropriate and provide effective control of toxicity).
- If toxicity remains clinically significant and does not recover to <Grade 2 within 15 days, the patient will be taken off-study.
- Only one dose reduction will be allowed per patient unless, in exceptional circumstances, the PI, Sponsor and patient agree that further treatment is appropriate and that a dose reduction is expected to provide effective control of toxicity.

Non-haematological toxicities:

Grade 2

- Patients who experience a clinically significant Grade 2 non-haematological toxicity related to BT1718 (probably or highly probably), that does not respond (<7 days) to supportive clinical management, will omit subsequent doses during that cycle until the toxicity resolves to <Grade 1 or baseline.
- If a clinically significant Grade 2 BT1718-related toxicity is still present when a patient is due to start the next cycle, that cycle should be delayed up to 14 days until the toxicity resolves to ≤Grade 1 or baseline.

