- The first time a dose is omitted or delayed, it may be given at the same dose when recommencing. However, if there is a subsequent need to omit or delay again, the dose should be reduced to a lower dose level (unless, in exceptional circumstance, the PI, Sponsor and patient agree that further dose omissions/delays are appropriate and provide effective control of toxicity).
- If toxicity remains clinically significant and does not recover to ≤Grade 1 or baseline within 15 days, the patient will be taken off-study.

• Only one dose reduction will be allowed per patient, unless, in exceptional circumstances, the PI, Sponsor and patient agree that further treatment is appropriate and that a dose reduction is expected to provide effective control of toxicity.

Grade 3

- Patients who experience a Grade 3 non-haematological toxicity that does not rapidly respond (<3 days) to supportive clinical management, will omit subsequent doses during that cycle until the toxicity resolves to ≤Grade 1 or baseline (or non clinically significant Grade 2).
- If clinically significant ≥Grade 2 BT1718-related toxicity is still present when a patient is due to start the next cycle, that cycle should be delayed up to 14 days until the toxicity resolves to ≤Grade 1 or baseline.
- When patients recommence treatment after a Grade 3 non-haematological toxicity, the dose should be reduced to a lower dose level. If toxicity does not recover to ≤Grade 1 or baseline within 15 days, the patient will be taken off-study.
- Only one dose reduction will be allowed per patient, unless, in exceptional circumstances, the PI, Sponsor and patient agree that further treatment is appropriate and that a dose reduction is expected to provide effective control of toxicity.

Grade 4

• Patients who experience a Grade 4 non-haematological toxicity, or liver enzyme changes consistent with Hy's Law (bilirubin >2x ULN and ALT/AST >3x ULN, with no explanation other than drug), will cease further treatment and be taken off-study once accuracy of testing is confirmed.

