5.7 Concomitant medication and treatment

Concomitant medication may be given as medically indicated. This includes symptomatic clinical management of BT1718 related or unrelated AEs. Vaccinations, including COVID-19 vaccines are permitted. Some vaccinations may be subject to specific Sponsor risk assessment. Details (including name and start and stop dates of the concomitant medication given) must be recorded in the patient's medical records and details entered into the electronic case report form (eCRF).

Palliative radiotherapy may be given concomitantly for the control of bone pain or other symptoms. These irradiated lesions will not be evaluable for response.

The patient must not receive other anti-cancer therapy or investigational drugs while on the trial.

As in Section 5.5 above, dosing with BT1718 may also be delayed up to 15 days if required to manage toxicity, without a patient needing to be withdrawn from study.

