- (f) In the event of a Grade 4 neutropenia or Grade 4 thrombocytopenia a full blood count must be performed at least on Day 7 (neutropenia) and Day 5 (thrombocytopenia) after the onset of the event to determine if a dose limiting toxicity has occurred. Continue close monitoring until resolution to Grade 3 or less.
- (g) To be repeated before biopsy procedure if done.
- (h) To be done Cycle 1 and 2, within 1 hour before and 1 hour (+15 mins) after BT1718 administration, then clinically indicated thereafter.
- (i) ECGs should be performed **before** BT1718 administration, and within **1** ½ hours (+15mins) after BT1718 administration during Cycle 1 Day 1. On Cycle 2 Day 1 an ECG should be performed **before** or within 1 ½ hours (+15 mins) after BT1718 administration. From Cycle 2 onwards ECGs should be repeated on Day 1 every two cycles.

- (k) Pharmacokinetic (PK) second sample collection refer to the Laboratory Manual for specific timings.
- (I) Unless performed within previous 28 days or PD seen on previous study scan.
- (m) Monthly **follow-up** required ONLY for those AEs and SAEs considered drug-related (highly probable, probable or possible) and present at off-study visit. Monthly follow-up to continue until resolution, return to baseline, stabilisation or patient starts another anti-cancer treatment.
- (n) All patients should be followed up for first progression and for survival until the end of trial. For those no longer on treatment, the site trial team should check the status of the patient at least three monthly (through NHS/HSC electronic data records or by phone calls only if appropriate) to determine when PD occurs (if not already occurred) and if the patient remains alive.

- (P) The timing of CT/MRI schedule may change in the expansion phase (Phase IIa) depending on tumour type. Any CR or PR needs to be confirmed by a subsequent assessment at least four weeks later.
- (q) Assessments may continue until disease progression or for up two years and can be performed more frequently than every two cycles, if clinical concern or suspicion of disease progression.
- (r) Temperature, blood pressure (seated or lying after 5mins rest) and pulse should be performed before and then repeated 1 hr (+/- 15 mins) after BT1718 administration.

NB: Phase I, Stage 1 is complete.

Observation/ Investigation	Pre screening	Pre treatme evaluations period)	ent s (screening	Cycle 1 (Cycle 2 onwards	Off study	Follow-up	Survival Follow-up

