The timing of CT/MRI schedule ma	ay change in the expansion phase (Phase IIa) depending on tumour type. Any CR or PR needs to be confirmed by a subsequent iter.
assessment at least four weeks la	
assessment at least four weeks la Assessments may continue until d disease progression.	lisease progression or for up two years and can be performed more frequently than every two cycles, if clinical concern or suspicion of

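### Scheduled scans follow cycle number with no calendar anchor, so toxicity delays postpone scan-detected progression and repeated delays can bias the six-month PFS rate upward

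*Protocol*

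**What the plan says.** Section 10.2.2 states: "Tumour assessments must be repeated Day 15 – Day 28 of every two cycles or more frequently, when clinically indicated". Section 7.2.2 and the schedule table in Section 7.5.2 give the same cycle-based window. No section says what happens to a scan when a cycle starts late.

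On cycle length, Section 5.2.2 says: "Each cycle of treatment will consist of 28 days and patients may continue until disease progression". On toxicity still present at the next cycle start, Section 5.5.1 says: "that cycle should be delayed up to 14 days until the toxicity resolves". More than one delay is foreseen. For haematological toxicity the same section says "The first time a dose is omitted or delayed, it may be given at the same dose the next time", and it then links a further delay to a reduced dose. Section 5.7 restates the limit differently: "dosing with BT1718 may also be delayed up to 15 days if required to manage toxicity".

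Footnote (p), which appears in both schedule tables, adds: "The timing of CT/MRI schedule may change in the expansion phase (Phase IIa) depending on tumour type". It names no interval. Its second sentence carries the requirement to confirm CR and PR.

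Section 3.1.2 lists PFS and the six-month PFS rate among the secondary endpoints. Section 13.6 measures PFS from trial entry to documented progression or death.

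**The concern.** Progression that shows only on imaging takes its date from the scan that finds it. If scans move with the cycles, that date depends on how often a patient's treatment was held for toxicity as well as on the disease. A patient with more delays is looked at later and, with the same true course, is recorded as progressing later. The distortion is therefore linked to tolerability, and more patients would not remove it. It also arises when the data are collected: an analysis plan written later cannot supply scans that were never done. The six-month rate is the figure most exposed, because the third scheduled scan falls shortly before that landmark.

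**Working it through.** The plan states no sample size, event count or power for PFS, so there is no figure of its own to reproduce. The check has two parts.

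**1. Scan days.** Inputs from the protocol: 28-day cycles (5.2.2), scans on Days 15–28 of every second cycle (10.2.2), and delays of up to 14 days per cycle start (5.5.1). With cumulative delay D before the scan in cycle k, the window runs from day 28(k−1)+15+D to day 28k+D, counting first dose as day 1.

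| 14-day delays before the scan | Cycle 2 | Cycle 4 | Cycle 6 |
|---|---|---|---|
| None | 43–56 | 99–112 | 155–168 |
| One | 57–70 | 113–126 | 169–182 |
| Two | not possible | 127–140 | 183–196 |

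Six months is 6 × 30.4375 = 182.6 days, and study day d lies d−1 days after first dose.

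- One delay: the third scan falls 168–181 days after first dose, still inside the landmark.
- Two delays: it falls at 182–195 days, so all but the first day of the window is past the landmark. The Cycle 4 scan, at days 99–140 depending on when the delays occurred, is then the last scheduled look.
- The undelayed window is 154–167 days after first dose. Its last day passes 182.6 once the delay reaches 183−167 = 16 days, and the whole window does so at 183−154 = 29 days.
- With the 15-day limit of Section 5.7, two delays give days 185–198 and the same reading.

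PFS starts at trial entry, not first dose. If entry precedes dosing by 7 days (an assumption), one delay puts the third scan 175–188 days after entry, and 6 of its 14 possible days (183–188) are past six months.

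**2. Effect on the six-month rate.** The following are assumptions, not in the documents: exponential PFS; delays of exactly 14 days at random cycle starts 2 to 6; scans uniform over the window; gap from entry to first dose of 0, 3 or 7 days; a stated share of progressions found only by scheduled scan. Each scenario used 400,000 simulated patients. The table is for a true median of 3 months, where the true six-month rate is 25.0%. Entries are the measured rate in %, with the change from no delay in points.

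| Scenario | Gap 0 | Gap 3 | Gap 7 |
|---|---|---|---|
| No delay | 29.6 | 29.0 | 28.1 |
| One delay in every patient | 26.8 (−2.8) | 28.4 (−0.6) | 32.0 (+3.9) |
| Two delays in every patient | 38.9 (+9.3) | 38.9 (+9.9) | 37.8 (+9.7) |
| 30% one delay, 20% two | 30.6 (+1.0) | 30.7 (+1.7) | 31.2 (+3.1) |
| No delay, half of progressions found clinically | 27.2 | 26.9 | 26.4 |
| Same mix, half found clinically | 27.8 (+0.6) | 27.8 (+0.9) | 28.1 (+1.7) |

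One delay with no gap lowers the rate because the third scan then sits closer to the landmark and catches progressions that an earlier scan would miss. For true medians of 2, 4 and 6 months, two delays in everyone add about 8 to 10 points and the mix adds about 1 to 3.

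**Scale.** One patient in 16 is 1/16 = 6.25 points. The exact 95% interval for 5/16 is 11.0–58.7%, about 48 points wide.

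**After anchoring to first dose.** The third scan stays at days 155–168 for everyone, and the measured rate returns to the no-delay row. About 2 to 5 points above the true rate remain over the medians tried, because the last scan precedes month six. That is ordinary interval-assessment bias and does not depend on toxicity.

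**The case against.** A reader might infer that any toxicity delay inflates six-month PFS. The documents do not support that. By the protocol's own day counts, a single full delay leaves the third scan inside six months from first dose, and it can lower the measured rate. Doses omitted within a cycle do not move the scan at all.

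The protocol also limits the effect. Section 7.2.2 allows earlier scans on clinical concern, and Section 10.2.2 requires re-evaluation when a patient leaves for reasons other than progression, unless assessed in the previous four weeks. Death counts as a PFS event. Section 5.5.1 takes patients off study if clinically significant toxicity does not recover within 15 days, and it normally allows only one dose reduction, which makes long runs of delays less likely. All of this stands and is why the effect is modest.

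A reader might also infer that footnote (p) contradicts Section 10.2.2, or that it makes PFS non-comparable between the cohorts. It is a permissive exception beside a default schedule and sets no differing interval for any cohort. Data are descriptive and reported by cohort, with no between-cohort PFS comparison planned, and the oesophageal cohort may never open. The footnote plays no part in the delay effect. What stands is narrower: it leaves an interval open that would affect PFS if used.

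Finally, no PFS benchmark or decision rule exists; the activity benchmarks in Section 13.1 use objective response. That lowers the priority. It does not remove the mechanism, which follows from carrying out the plan exactly as written.

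**Conclusion.** The point holds in limited form. Scheduled scans have no calendar anchor, so each cycle delay postpones every later one, and scan-detected progression is dated later in patients with more toxicity. The six-month PFS rate is biased upward by this only when enough delay accumulates: about two full delays counted from first dose, less if trial entry precedes dosing. At an assumed 3-month median, with all progressions found by scheduled scan, the shift is about +9 to +10 points if every patient had two delays and about +1 to +3 points in the assumed mix. It runs from −2.8 to +3.9 points if every patient had one.

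These sizes rest on exponential PFS and on delay frequencies that the protocol does not give. Against an interval some 48 points wide in a cohort of 16, the effect is modest, and the change is a worthwhile improvement rather than a necessity. No effect on duration of response was quantified.

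**What to change.** In Sections 7.2.2, 7.5.2 and 10.2.2, keep the present frequency and window but count from first BT1718 dose: study days 43–56, 99–112 and 155–168, then every 8 weeks while on study, irrespective of cycle delays. Keeping this window matters. An undelayed Cycle 3 starts on day 57, so patients without delays are still scanned before it. Day 43 is 42 days after first dose, so the six-week minimum for stable disease is also still met.

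Limit the tumour-type sentence of footnote (p) to additional scans. Do not delete the whole footnote, because it also carries the CR/PR confirmation requirement in the schedule tables.

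The cost is amendment wording, with the same nominal scan frequency and no change to any treatment rule. The downside is that after a delay a scan may fall mid-cycle and after fewer doses. For example, a 14-day delay to Cycle 2 makes days 43–56 its Days 1–14. Sites must also schedule by calendar. Separately, the 14-day limit in Section 5.5.1 and the 15-day limit in Section 5.7 must be reconciled.

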10.3 Tumour response

All patients who meet the eligibility criteria and receive \geq 66% of the planned dose exposure of BT1718 within Cycle 1 and 2, or at least one full cycle and have a baseline assessment of disease and at least one repeat disease assessment will be evaluable for response. Patients who develop clear evidence of PD without a formal disease assessment will be considered non-responders. Confirmatory repeat assessments are required at least four weeks after an initial indication of CR or PR, in order for the

patient to be assigned a status of confirmed CR or PR. To be assigned a status of SD, follow-up measurements must have met the SD criteria at least once and at least six weeks after the initial dose of BT1718 is given.

Should rapid tumour progression occur before the completion of four weeks the patient will be classified as having early progression.

Tumour response should be classified as "not evaluable", only when it is not possible to classify it under another response category, for example, when baseline and/or follow-up assessment is not performed or not performed appropriately.

Expert reviewers appointed by the Sponsor may undertake an independent review of the Investigator's assessed objective responses (CR and PR). The expert reviewers will include at least one specialist who is not an Investigator in the study. Any independent reviewer's assessment will also be documented in the final CSR along with the assessment made by the Investigator. The eCRF will reflect the Investigator's opinion.

